## Research Strategy and Study Design

### Study Overview:

During the 4-year study period we will screen 200 SCI participants who meet eligibility criteria and consent to participate with portable level II polysomnography (PSG) and randomize 100 subjects who have SDB to auto-PAP or sham PAP. Participants will be recruited from the University of Miami (Miami Project to Cure Paralysis), the Miami VA, Wayne State University (Michigan Rehabilitation Institute), and affiliated Detroit VA through their outpatient SCI clinics and/or inpatient rehabilitation units. Participants will be asked to complete questionnaires measuring sleep quality (SQ), SDB risk, insomnia severity, daytime sleepiness, pain severity, mood, and HRQOL. They will undergo an overnight, at home (or if hospitalized, in the hospital room) portable unattended PSG performed at their normal sleep time. Subjects with an apnea-hypopnea index (AHI)  $\geq 10$  events/hr will be randomized to receive 4 months of auto-PAP therapy or PAP set at a fixed pressure of 3 cmH20 (sham PAP).

We will perform neuro-psychological evaluations prior to randomization on all participants who complete a portable PSG to evaluate general and pre-morbid function, immediate verbal memory, simple and sustained attention, processing speed, and executive function. Selection of these particular cognitive measures reflects impairments in these domains observed in patients with SDB within the general population. These domains are also impaired in patients with acute and chronic SCI. **Importantly, none of the cited SCI studies have examined the potential role of SDB in cognitive impairment in SCI participants.**

One cognitive measure (PASAT) and 3 sleep questionnaires (PSQI, FOSQ and ESS) will be repeated at 1 month follow-up in those randomized to therapy or placebo. Complete neuro-psychological evaluations will be repeated at the 4 month follow-up time point in those with SDB who were randomized to PAP or sham PAP (primary outcomes). All measures obtained from these repeated assessments will be subject to a Reliable Change Index analysis to control for potential practice effects. We will obtain blood and urine samples for measurement of CV biomarkers at time of randomization and the four month follow-up. Additionally, sleep and quality of life questionnaires will be repeated at four month follow-up (secondary outcomes).

### Study Population:

We will perform unattended portable level II PSG on SCI participants from the Miami and Detroit study sites (100 from each site) who meet the following eligibility criteria:

*Inclusion Criteria:*

- Chronic tetraplegia or paraplegia (C4-L1), American Spinal Injury Association (ASIA) Impairment Scale A, B, C and D
- 18 years and older
- At least one year post injury
- Hearing and vision suitable for comprehension of instructions, and perception of cognitive test stimuli
- No color blindness as measured by a brief screen with color perception Ishihara cards
- Stable medical condition for 2 weeks prior to enrollment. Patients admitted to hospital will be eligible for enrollment if the acute illness precipitating admission is in recovery phase for 2 weeks or longer

*Exclusion Criteria:*

- Diagnosis of SDB and successful positive airway pressure (PAP) therapy prior to injury. Those with a diagnosis of SDB post injury who are not receiving therapy for SDB (PAP, surgical, and/or oral appliance) are eligible for study enrollment
- Patients who are intubated, have a tracheostomy, and/or are using long term invasive/non-invasive positive pressure ventilation
- Participants with predominant central sleep apnea on PSG requiring bi-level PAP therapy
- Severe traumatic brain injury (GCS < 8 at first assessment)
- Unable to understand or read English at a grade 5 level
- Inability to provide informed consent
- Evidence of advanced neurological or systemic disease that may affect cognitive functioning (e.g., Alzheimer's disease, Dementia, Parkinson's disease)
- Significant aphasia or language impairments

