	
function. These deficits are important for day to day activities.
 
SCI participants with SDB may indeed demonstrate worse cognitive impairment in these domains.
 
More study is needed to determine the full extent of the interaction between SDB and SCI and their combined impact on cognitive function.
	
results between those with and without SDB.
 
b) Additionally, other factors that may impact cognitive performance including pain severity, mood, pre-morbid intelligence, duration of injury, presence of insomnia, and use of sedating medications will be measured and included in a multivariable regression model to better delineate the impact of each of these factors and SDB on cognitive impairment.

1 and 2	
Although there is now some data that demonstrate increased prevalence of poor sleep quality and SDB in SCI subjects, there is no clear evidence that treating these conditions will lead to short and long term benefits.
 
PAP is a medically-justified intervention in persons with SDB, but has seen limited use in persons with SCI. Strength of evidence does not currently support screening for SDB and intervention with PAP in persons with SCI.
 
Persons who are prescribed PAP are not always compliant with its use. Compliance in this population has seen limited study.
 
The impact of PAP on cognitive outcomes in chronic SCI is unknown
 
The impact of PAP on surrogate CV biomarkers, mood, and quality of life in this population is unknown.
	
a) The research will determine the effectiveness of PAP in treating SDB in chronic SCI using gold standard research methodology (RCT).
 
b) The research will provide the empirical support necessary to justify treatment of SDB in persons with SCI.
 
c) The research will examine population-specific compliance levels in PAP use, and identify whether compliance influences health-related outcomes.
 
d) Our clinical trial will identify the impact of PAP therapy on cognitive measures, mood, quality of life, and surrogate CV endpoints. All these measures are relevant to the emotional and physical well-being of participants with chronic SCI and will likely have a practical impact on day to day living in this population.

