### Objectives/Specific Aims/Hypotheses

The proposal describes a multi-center double blinded, placebo controlled randomized trial (RCT) designed to examine the impact of SDB treatment in persons with chronic SCI. The **central hypothesis** is that the treatment of SDB with PAP will improve cognition, sleep quality, HRQOL, and CVD surrogate measures in persons with chronic SCI. The specific aims and hypotheses of the proposed research are:

Specific Aim 1	
Determine the associations between sleep disordered breathing (SDB) and cognitive impairments in chronic SCI and the impact of PAP therapy on cognitive measures in a cohort with chronic SCI and SDB.
 
Hypothesis 1a: Compared with patients without SDB, patients with SDB will exhibit more severe and widespread cognitive impairments (in memory, attention, and executive function), while controlling for depression, pain severity, duration of injury, level of injury, sedative use, and pre-morbid intelligence
 
Hypothesis 1b: SCI participants who are randomized to four months of therapeutic PAP will show improvement in cognitive measures (memory, attention, and executive function) compared with those receiving sham PAP.

Specific Aim 2	
Determine the impact of PAP therapy on surrogate CV biomarkers, sleep quality, quality of life, mood, and pain in a cohort with chronic SCI and SDB.
 
Hypothesis 2a: SCI participants randomized to four months of PAP will show an improvement in CV biomarkers (hs-CRP, TNF-a, VCAM-1, adiponectin, and 8-isoprostanate) compared with sham PAP.
 
Hypothesis 2b: Sleep quality, quality of life, mood, and pain will improve in SCI participants receiving PAP and stay the same or worsen in those randomized to sham PAP.

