### **Data Analysis:**

Feasibility: The SCI Service at Miami VA actively serves approximately 300 patients. The Miami Project maintains a database of persons who have volunteered their participation in research studies and a database of individuals who have participated in past studies and volunteered additional participation. The database currently contains 3400 persons whose ages and levels of injury match the sought study participants. The Detroit VA SCI service oversees the care of greater than 100 patients/year. The Rehabilitation Institute of Michigan provides care for 350 SCI individuals. We anticipate completion of enrollment by the second quarter of Year 4, with 100 patients enrolled for PSG from each site.

Sample size justification and power: We will recruit 200 participants who meet our eligibility criteria and anticipate an SDB prevalence of 0.50 in SCI participants. This will allow us to randomize 100 participants with SDB to PAP or placebo arm. The neurocognitive test best characterized in both SCI and SDB is the Paced Serial Addition Test (PASAT). The PASAT is our primary study outcome. A mean difference in PASAT scores of 7 discriminates between those with and without cognitive impairment in populations with and without SDB. Assuming a standard deviation of 9 and alpha of 0.05, a sample size of 40 per study arm has a power of 0.93 to detect a mean difference of 7 units. Assuming a PAP non-adherence rate and/or loss to follow-up of 40%, we will continue to have sufficient power (81%) to detect such a difference with our proposed sample size of 100. These findings would be in keeping with PASAT values obtained in non-disabled patients with SDB vs. controls, and PASAT performance in other populations (e.g. multiple sclerosis, mild traumatic brain injury).

Planned analyses: We will score questionnaires while blind to PSG data and group allocation using instructions provided by the questionnaire developer. We will first examine continuous variables for normality. For those variables without a normal distribution, we will explore appropriate transformations in an attempt to achieve normality. Continuous variables will be summarized as means and SD, and categorical variables will be summarized as frequencies. Prevalence of poor SQ will be calculated as the proportion of individuals who complete the PSQI with a score of  $\geq 5$ .

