Prevalence of insomnia will be calculated as the proportion of individuals who complete the AIS with a score  $\geq 6$ . Prevalence of SDB will be calculated as the proportion of individuals who undergo PSG with AHI  $\geq 10/\text{hr}$ .

To determine baseline associations between SDB and cognitive measures (Hypothesis 1a), we will develop Generalized linear models (GLM), with each of the cognitive variables as dependent variables and presence or absence of SDB as an independent variable. The analyses will be repeated with AHI or ODI4 (measures of SDB severity) as independent variables. We will control for other co-variates including age, depression, anxiety, HRQOL, pain severity, duration of injury, level of injury, use of sedating medications, and presence of insomnia. For all GLM developed, the data may be transformed to meet the normality and homogeneity of variance assumptions of the analysis.

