#### Primary Hypothesis (Specific aim 1, Hypothesis 1b)

A test of the primary null hypothesis, that PAP intervention does not increase mean PASAT score against the 1-sided alternative hypothesis that PAP intervention increases mean PASAT, will be based on a general linear model (GLM). PASAT score is modeled as a function of PAP intervention, using an indicator variable with 1 indicating PAP and 0 the sham treatment. A 1 degree of freedom test based on an F statistic will be used to test for a positive coefficient for the PAP indicator. This modeling approach provides a unified framework that accommodates covariates including use of sedating medications, years of education, level of injury, duration of injury, pain severity, presence of anxiety or depression, compliance with PAP, and recruitment center, each of which may reasonably be anticipated to influence PASAT score. We plan to include these covariates in our primary hypothesis test, which will be carried out at  $\alpha = 0.05$ . If the null hypothesis of no effect is rejected, computation of 95% confidence limits on the estimate of treatment difference in PASAT score mean will be carried out.

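### Hypothesis 1a has no adjustment for lesser brain injury, which stays eligible, so it could credit sleep disordered breathing with deficits from the original trauma

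*Combined protocol and SAP*

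**What the plan says.** All references are to the combined protocol and SAP.

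- **Eligibility (Study Population, Exclusion Criteria).** The single criterion on brain injury is "Severe traumatic brain injury (GCS < 8 at first assessment". A score of 8 or above does not exclude. The other criterion that touches cognition is "Evidence of advanced neurological or systemic disease that may affect cognitive functioning (e.g., Alzheimer's disease, Dementia, Parkinson's disease"; its examples are degenerative, and it does not clearly reach a past mild or moderate head injury.
- **Hypothesis 1a as stated (Objectives/Specific Aims/Hypotheses).** The comparison is made "while controlling for depression, pain severity, duration of injury, level of injury, sedative use, and pre-morbid intelligence".
- **Hypothesis 1a as modelled (Data Analysis, Planned analyses).** "We will control for other co-variates including age, depression, anxiety, HRQOL, pain severity, duration of injury, level of injury, use of sedating medications", and insomnia.
- **Purpose of the adjustment (Study Relevance and Applicability of Proposed Findings).** The plan undertakes to measure and model "other factors that may impact cognitive performance including pain severity, mood, pre-morbid intelligence, duration of injury, presence of insomnia, and use of sedating medications", so that their effects can be told apart from that of SDB.
- **PASAT benchmark (Data Analysis, Sample size justification and power).** The 7-point difference is described as agreeing with "PASAT performance in other populations (e.g. multiple sclerosis, mild traumatic brain injury".
- **Literature cited.** References 33 and 77, used to support the statement that cognition is impaired after spinal cord injury (SCI), have titles about closed head injury in SCI patients.

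**The concern.** Hypothesis 1a is a cross-sectional comparison of people with and without SDB. Randomisation does not protect it, so it depends on measuring and modelling the other causes of poor cognitive scores. Brain injury sustained with the cord injury is an obvious candidate, and the protocol's own text and reference list point to it, but no Hypothesis 1a list contains it.

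None of the listed covariates substitutes for it. Level and duration of injury describe the cord lesion. The reading test is a proxy for ability before the injury.

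If lesser brain injury were more frequent in the SDB group after adjustment, the SDB coefficient would absorb its deficit. The trial would then report an association that partly reflects the original trauma, a component that treating SDB would not be expected to reverse.

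**Working it through.** **1. Is brain injury in any covariate list?** There are three lists for Hypothesis 1a (the hypothesis statement, the study-relevance table, Planned analyses) and one for Hypothesis 1b ("covariates including use of sedating medications, years of education, level of injury, duration of injury, pain severity, presence of anxiety or depression, compliance with PAP"; the study site completes it). None names brain injury, GCS or loss of consciousness. Baseline Measurements provides for recording co-morbidities from medical records, but does not name brain injury and does not carry it into a model.

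**2. Inputs the documents give.** PASAT difference 7, SD 9, and SDB prevalence 0.50 of 200 screened, so about 100 with and 100 without SDB. The plan has no figure for brain injury. As a check on the borrowed inputs, its power at 40 per arm reproduces:

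- SE = 9 × √(2/40) = 2.012, and 7/2.012 = 3.478.
- Power, two-sided 5%, normal approximation = Φ(3.478 − 1.960) = 0.936. The t test gives 0.930, against 0.93 stated.

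**3. Inputs the documents do not give (assumed).**

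- Excess of lesser brain injury in the SDB group, Δp: 0 to 30 percentage points. Zero belongs in the range. A negative Δp is also possible and would hide a true SDB effect.
- Mean PASAT deficit from lesser brain injury, d: 3.5 to 7 points. The 7 is borrowed; the plan uses it to separate impaired from unimpaired people, not as the deficit from brain injury.

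**4. Spurious SDB difference.** Bias = Δp × d, before any adjustment. SE = 9 × √(2/100) = 1.273. If SDB has no true effect, the chance of a nominally significant two-sided result is Φ(bias/SE − 1.960) + Φ(−bias/SE − 1.960).

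| Δp | Bias, d = 3.5 | False-positive rate | Bias, d = 7 | False-positive rate |
|---|---|---|---|---|
| 0 | 0 | 5.0% | 0 | 5.0% |
| 0.10 | 0.35 | 5.9% | 0.70 | 8.5% |
| 0.20 | 0.70 | 8.5% | 1.40 | 19.6% |
| 0.30 | 1.05 | 13.1% | 2.10 | 37.8% |

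For example, 0.20 × 7 = 1.40; 1.40/1.273 = 1.10; Φ(−0.86) + Φ(−3.06) = 0.196.

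The largest bias is 2.1/7 = 30% of the benchmark, and it needs both assumptions at their extremes. The listed covariates, level of injury among them, would remove an unknown part.

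**5. Hypothesis 1b.** Allocation is randomised 1:1 within center, so expected Δp between arms is zero and so is the expected bias. What remains is variance. With a share p of participants affected, the fraction of variance explained is p(1 − p)d²/81:

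- p = 0.2 to 0.4 and d = 7: 0.097 to 0.145.
- p = 0.2 to 0.4 and d = 3.5: 0.024 to 0.036.

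Removing even the largest share (residual SD 9 × √(1 − 0.145) = 8.32) moves power at 40 per arm only from 0.936 to about 0.96.

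**The case against.** The strongest reply is that the confounding path is not documented. Bias needs lesser brain injury to be more common with SDB after adjustment, and no section says so. A reader might infer a route through cervical injury, because the Background cites a study linking sleep apnea to a higher cervical level. The documents do not carry that inference: the next study cited found no correlation with lesion level, nothing in the text ties cervical injury to brain injury, and level of injury is already a covariate. This reply stands as a limit on the claim. It leaves the bias possible, not shown.

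A reader might also infer that the protocol states outright that mild brain injury lowers PASAT. It does not. It says the expected difference agrees with performance in that population, which implies a reduction without giving its direction or size. References 33 and 77 can be judged here by title only.

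It is also fair to say that the lists are open-ended, that co-morbidities are recorded, and that some people with lesser brain injury would fail other criteria (consent, aphasia, reading level). So the plan does not forbid the adjustment. But a covariate that is not named is not pre-specified, and one chosen after the data are seen persuades less.

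Finally, old records may lack a GCS, and GCS alone separates no injury from mild injury poorly. That weakens the remedy without removing its value.

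**Conclusion.** The point holds as a modest gap in Hypothesis 1a: lesser brain injury is eligible, is signalled by the protocol's own text as relevant to PASAT, and is absent from every Hypothesis 1a covariate list. Whether it biases the SDB comparison cannot be settled from the documents. The range of 0 to 2.1 PASAT points illustrates what assumed inputs would do before adjustment; it is not an estimate, and zero is a legitimate value.

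A reader might infer that the primary treatment comparison is compromised too. It is not: randomisation balances brain injury in expectation, and the possible gain is a little precision. A stable deficit from an injury at least a year old would also show in the baseline PASAT, which is already collected and would be a more direct adjustment. The plan names the PASAT treatment effect as its main inference, so this is a cheap improvement to a supporting analysis and no threat to the primary result.

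**What to change.** 1. Retain first-assessment GCS, which the exclusion already requires to be looked up, and documented loss of consciousness where available, as one baseline variable with levels none, mild, moderate and unknown. Write the boundaries down in advance, including where a score of exactly 8 falls.
2. Add this variable to the Hypothesis 1a models in Planned analyses.
3. Add one Hypothesis 1a sensitivity analysis restricted to participants with no recorded brain injury, and report it beside the main result.
4. Leave eligibility and the Hypothesis 1b model as they are.

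The cost is one retained data item and up to 3 degrees of freedom in a sample of about 200. The weaknesses are missing GCS in old records, which the unknown level handles but does not cure, and coarse classification, so some residual confounding could remain. The number in the unknown level should be reported so that readers can judge how much the adjustment achieves.

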**Randomization Protocol**

Participants who meet above eligibility criteria and are diagnosed with SDB with AHI  $\geq 10$  will be randomized to treatment with either auto-PAP or fixed PAP set at 3 cmH2O (sham PAP). It is anticipated that 100 participants will have AHI  $\geq 10$  (50 from each site) and undergo randomization to treatment or placebo in a 1:1 ratio within each center.

The randomization sequence will be generated by the study statistician using a computer-generated random-number table. The randomization numbers will be placed in serially numbered, sealed, opaque envelopes available to the study PI/site PI. The study coordinator from each site will request an envelope to be opened by the PI at the time of randomization. The study coordinator and the participants will be blinded to treatment assignment. Interpretation of study results will occur blind to study arm assignment.

**Intervention**

All randomized subjects will be fitted with a nasal or full-face mask and head gear. PAP will be delivered by an auto-titrating device (Resmed S9-Autoset, San Diego USA). These devices automatically set the level of delivered pressure to ensure upper airway patency, to treat detected apneas and hypopneas, thereby eliminating the need for a pressure titration sleep study to be performed in the sleep laboratory. Auto-PAP has been successfully used in several patient populations and may improve compliance with PAP. Participants who are randomized to the placebo arm will receive an auto-PAP device that is set to a fixed low pressure of 3 cmH2O without an ability to titrate according to detected respiratory events. The pressure is too low to eliminate respiratory events and serves as sham or sub-therapeutic PAP (placebo PAP). Additionally, six extra

4 mm holes will be cut in the rubber collar of the connecting tubing at the mask end. These extra blow-off holes, together with the standard hole in the PAP mask, allow more air to escape and keep the nasal pressure low while ensuring no CO2 re-inhalation. This method has been successfully and safely used as a placebo in previous RCTs in participants with SDB.

The auto-PAP machines will record the number and type of respiratory events detected, the pressure delivered in response to these events and the amount of time that the machine was on and delivering pressure to a patient. All subjects will be instructed to use the device nightly during sleep, for the ensuing four months. Objective compliance checks will be conducted at 1 week, 1 month, and study completion, by having the subject present the PAP "Smartcard" for download and interpretation. To increase patient compliance and decrease variance in outcomes introduced from differing degrees of exposure to the intervention, we will employ standardized procedures for management of PAP currently employed at University of Miami PAP clinic. These include instructing subjects on machine and mask use and regular phone follow-up for troubleshooting as necessary. The study PI will review compliance downloads and instruct the Research Associates (RA) to contact participants if compliance is low or machine reported air leakage from mask is too high. This is will be done for both arms of the study. The RA will not be aware of the details of the compliance report or machine pressure delivered to maintain blinding. Daily compliance will be reported as the total number of hours of PAP use per 24 hour period. Patients who use PAP > 4 hours/night for more than 50% of the nights at 4 month follow-up will be classified as PAP compliant.

**Baseline Measurements All Subjects:** At the Miami and Detroit sites the study RA will approach SCI individuals identified by the study PI and Co-investigators to determine eligibility for participation in the study. Upon consent, we will ask participants to complete several questionnaires detailed below. We will schedule participants for a single night unattended portable home PSG within one week of enrollment to evaluate sleep architecture and diagnose SDB. The RA at each site will review medical records to document medical and psychological co-morbidities, medication use, laboratory data, spinal cord injury level, ASIA classification, and duration of injury. We will interview participants during their enrollment visit to obtain a medical/sleep history, and anthropometric measures (height, weight, neck circumference, and abdominal girth at end expiration). Whenever possible the RA or PI/site PI will complete the international SCI core dataset for each participant. Additionally, we will use the international SCI CV function basic data set to obtain information about CV co-morbidity. Cognitive testing will be completed at baseline on all subjects who complete portable PSG. **Figure 2 outlines study flow and measurements.**

We will obtain the following respiratory measures during PSG: a) AHI: defined as the number of apneas and hypopneas per hour of sleep, b) arousal index (AI): the number of arousals per hour of sleep, c) percentage of total sleep time (TST) spent with arterial oxygen saturation (Sa-O2) < 90%, d) mean minimum Sa-O2, and e) oxygen desaturation index 4% (ODI4), defined as the number of four percent desaturation events per hour of study time. Respiratory and sleep architecture definitions will be scored according to accepted criteria put forth by the American Academy of Sleep Medicine (AASM). We will define SDB as an AHI  $\geq 10$ . We will score hypopneas initially using alternative rules (>50% reduction in airflow with 3% desaturation or arousal). We will rescore using recommended rules (>30% reduction in airflow with 4% desaturation). In the sleep research community, there is currently no clear consensus on which scoring method is preferred. SDB prevalence rates reported in the literature differ depending on the definition used. Consequently, we will perform all analyses with both definitions in mind and report any differences in observed associations.

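### The PI who orders adherence contacts is not stated to be blinded and has no numeric trigger, so support for PAP use could differ by arm

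*Combined protocol and SAP*

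**What the plan says.** The closing part of the Background and the opening of the Objectives both describe a double-blinded randomized trial.

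Randomization Protocol keeps the assignments in "sealed, opaque envelopes available to the study PI/site PI" and continues: "The study coordinator from each site will request an envelope to be opened by the PI at the time of randomization". On masking it states: "The study coordinator and the participants will be blinded to treatment assignment". It adds that results will be interpreted blind to arm. No PI is listed as blinded.

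Intervention says the machines record respiratory events, delivered pressure and time in use. Compliance is checked at 1 week, 1 month and study completion. On follow-up: "The study PI will review compliance downloads and instruct the Research Associates (RA) to contact participants if compliance is low". The second reason for contact is that "machine reported air leakage from mask is too high". Three safeguards stand beside this: "This is will be done for both arms of the study"; the Miami PAP clinic's standard management routine is to be followed; and the RA is not shown the report details or the pressure. The section's one numeric compliance rule (over 4 hours on over half of nights) classifies participants at month 4.

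**The concern.** Phoning participants whose use is low is a co-intervention, and the protocol says its support procedures are meant to raise compliance. A sham-controlled trial needs that support to be delivered without regard to arm. Here the choice of whom to contact rests with someone who is not stated to be masked and who works without a written threshold.

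If contacts differ by arm, the PAP-sham contrast compares device plus support with sham plus a different amount of support. Intention-to-treat analysis does not correct this, because the support becomes part of what each arm received. The documents call for no record of contacts, so an imbalance could be neither seen nor reported afterwards.

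**Working it through.** The plan gives no figure on this point, so there is nothing to reproduce. The check is to set the sections side by side.

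1. **Is the decision-maker masked?** The PI opens the envelope. Those named as blinded are the coordinator and participants (Randomization Protocol), the RA with respect to the downloads (Intervention), and the scorer of the cognitive tests (end of the Specific Aim 1 protocol). The study PI, who reads the downloads, is in none of these groups.

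2. **Does it matter that there are two PIs?** The envelopes go to the study PI or site PI, but the downloads go to the study PI. With 50 of the 100 randomized participants expected at each site, opener and reader may be different people for the Detroit half. The reader is still not stated to be masked. The device also records pressure and events, and the sham runs at a fixed 3 cmH2O without titration, so a full download could reveal the arm. The protocol does not say which of the recorded fields the compliance download displays.

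3. **Is the trigger fixed?** Neither low use nor high leak has a number in the documents, and phone troubleshooting is on an as-needed basis. The month-4 rule classifies participants; it does not start a contact.

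4. **When can the choice change exposure?** Of the three downloads, the one at completion is too late. Two remain per participant, so about 100 × 2 = 200 contact decisions if all 100 stay in the trial.

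5. **What do the safeguards cover?**

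| Safeguard | What it protects | What it leaves open |
|---|---|---|
| Review in both arms | Neither arm goes unreviewed | The same threshold in each arm |
| Clinic's standard routine | Content of support | When a contact is triggered; no threshold is given in the documents |
| RA masked | The person making the call | The choice of whom to call |
| Blinded scoring and interpretation | Measurement and reading of results | Exposure and support during the four months |

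6. **Is the leak trigger neutral?** Under Intervention the sham tubing has six extra 4 mm holes at the mask end. Machine-reported leak may therefore differ by arm by design. The documents do not say by how much.

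7. **Where would a difference enter the results?** It could enter through PAP exposure itself and through the compliance comparison promised in the Study Relevance table ("The research will examine population-specific compliance levels in PAP use, and identify whether compliance influences health-related outcomes"). It could also enter through compliance with PAP, a covariate in the primary model (Primary Hypothesis), and through the self-reported sleep, mood and quality-of-life outcomes, which may respond to attention as well as to treatment.

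**The case against.** The strongest defence is that the plan already does much of what is needed. Review covers both arms, a standard clinic routine is adopted expressly to limit variation in exposure, and the caller is masked. The primary outcome is a performance test with computer-paced items and blinded scoring. The self-reported outcomes most open to extra attention are declared exploratory. Randomization Protocol also discloses who is blinded, so nothing is hidden. All of this stands and limits the concern. It does not mask the person choosing whom to contact, and the clinic routine cannot be credited with a threshold that the documents do not show.

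A reader might infer several stronger points that the documents do not support:

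- **One person opens every envelope and reads every download.** At Detroit this is not established.
- **Contacts are decided case by case.** The text does not say so; it only lacks a stated threshold.
- **The per-protocol set is defined by compliance.** The plan mentions a per-protocol repeat of the analyses but defines no set.
- **The bias can be sized in PASAT points.** One could take the 7-point difference from the sample-size paragraph, assume 60% adherence and benefit only in adherent users, and obtain 7 × 0.60 = 4.2 points, with 7 × 0.10 = 0.7 points per 10-percentage-point shift in adherence. But the 7 points is described as separating people with and without cognitive impairment, not as the effect in adherent users. The 40% allowance covers non-adherence and/or loss to follow-up, so 60% is not an adherence figure. On the same assumption an ineffective device gives 0 × any adherence = 0. The sum describes dilution of a true effect, not a false one.

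**Conclusion.** The concern holds as a gap in masking and procedure. A PI not stated to be blinded selects participants for adherence contact on criteria without numbers, in a trial described as double-blinded. Support could therefore differ by arm after the 1-week and 1-month downloads.

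The size of any difference is unknown, and no PASAT figure should be attached to it. Nothing shows that contacts would in fact be uneven. The conclusion rests on two readings of the text: that silence about the PI means the PI is not masked, which the envelope procedure supports, and that no contact threshold exists outside the documents. If the clinic routine contains a fixed threshold, the discretion narrows, but the reader would still be unmasked. This is a worthwhile, inexpensive improvement, not a fatal flaw.

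**What to change.** In the Intervention section:

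- Pre-specify one contact criterion for use and one for leak, identical in both arms, with values set by the investigators.
- Have the criteria applied automatically, or by an existing team member masked to arm, from a report that omits arm, pressure and respiratory events.
- Show leak only as a flag, because the sham tubing may make the raw reading differ by arm. A flag could still be raised more often in one arm, which is a further reason to count contacts.
- Let the PI keep the full device data for safety.
- Log contacts per participant, with the reason, and report them by arm.

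In the design description, state that the PI is not blinded and list who is.

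The cost is protocol wording, a report template and a contact log. The PI loses some discretion over borderline contacts.
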